University of Kansas Medical Center
RESEARCH PROTOCOL INVOLVING HUMAN SUBJECTS TEMPLATE

Version date: October 1, 2018

Principal Investigator: [name], MS

Study Title: An open-label pilot study of the effect of intra-articular bilateral knee injections of Zilretta on OARSI recommended physical performance measures in adults with symptomatic knee osteoarthritis.

Co-Investigator(s): [name]

I. Purpose, Background, and Rationale

A. Aim and Hypotheses

This study will be an open-label trial to determine the functional effects of bilateral IA injections of Zilretta into knee joints of 70 subjects with bilateral KL grade 2-4 symptomatic knee osteoarthritis (OA). Measurement and evaluation of outcomes at baseline, 6, 12 and 24 weeks will allow assessment of short and long-term effects, consistent with Osteoarthritis Research Society International (OARSI) and Outcome Measures in Rheumatology (OMERACT) recommendations.

The **primary** aim of the proposed study is to demonstrate the effect of IA injection of Zilretta on physical performance measures in adults with bilateral knee OA. We will test this primary study endpoint by assessing the change in OARSI recommended physical performance tests¹ (30-second chair standing test, 40m fast-paced walking test, stair ascent) 6, 12 (primary) and 24 weeks after treatment.

The secondary outcome will be the change in Knee Injury and Osteoarthritis Outcome Score (KOOS-PS) at 6, 12 (main) and 24 weeks after treatment. This will be captured using the patient-reported physical function short form.

The tertiary outcomes will be the change in KOOS-Quality of life subscale (QoL) and Numerical Rating Scale (NRS) for pain. While the primary outcomes will be defined at the 12-week follow-up, all outcomes will be assessed at the 6- and 24-week follow-up as well to define the course and trajectory of effects.

We hypothesize that people with bilateral symptomatic knee OA will experience significant improvement in physical performance, physical function and quality of life for at least 12 weeks following treatment. Based on research done using Zilretta in patients with knee OA, we anticipate that it will have a greater magnitude and duration of analgesic effect along with significantly fewer adverse events when compared to the rates reported for standard of care therapy (i.e. immediate release corticosteroid injection).²

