Preliminary Data: In previous clinical trials, Zilretta (triamcinolone acetonide extended-release) provided an extended and predictable release of triamcinolone acetonide as the biocompatible PLGA microspheres slowly degraded. A single IA dose of Zilretta resulted in less systemically bioavailable triamcinolone acetonide when compared to a matched dose of triamcinolone acetonide crystalline suspension (TAcS)⁷ due to slower release and absorption into the systemic circulation. By providing prolonged local exposure to triamcinolone acetonide while minimizing systemic exposure, IA injection of Zilretta is expected to have sustained anti-inflammatory and analgesic efficacy while minimizing adverse effects⁸. A prior clinical trial provided evidence for analgesic efficacy for knee OA, with a significant reduction in average daily pain (ADP) sustained through 12-week follow-up⁹.

Therefore, the **primary** aim of the proposed study is to demonstrate the effects of IA injection of Zilretta on physical performance in adults with bilateral knee OA. We propose to determine the change in OARSI recommended¹⁰ physical performance measures (30-second chair stand time, 40m fast-paced walking time, stair ascent time) along with patient-reported physical function (KOOS-PS) and quality of life (KOOS-QoL) at baseline and at intervals following bilateral knee injection of Zilretta. The expected deliverables of this research will be evidence regarding the effects of Zilretta on objective and patient-reported physical functional outcomes in patients with bilateral symptomatic knee OA.

C. Rationale

Disability due to knee OA is based on the inter-relationships of pathology (e.g. knee cartilage degeneration), impairments (e.g. pain), functional limitations (e.g. difficulties with standing from a chair, walking or using stairs), and disability (e.g. inability to participate in community). Biomedical research frequently focuses primarily on pathology and sometimes on impairments. However, there is an imperfect correlation between impairments and functional limitations. While the effect of Zilretta on pain has been explored, the effects on physical function and performance are incompletely understood.

II. Research Plan and Design

A. Study Objectives: The goal of this study is to evaluate the efficacy of Zilretta for improving physical performance, physical function, and quality of life.

B. Study Type and Design:

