This will be an open-label study to determine the functional effects of IA injection of Zilretta into bilateral knees of 70 subjects with KL grade 2-4 symptomatic knee OA. Measurement of OARSI recommended physical performance measures¹⁰, patient-reported physical function, quality of life and pain at baseline, 6, 12 and 24 weeks will allow assessment of short and long-term effects, consistent with OARSI and OMERACT recommendations. Adverse events will be monitored.

Each subject will participate for up to 24 weeks following the intra-articular Zilretta injection. Enrollment is expected to take approximately 6 months. Total study duration is expected to require at least 12 months.

C. Sample size, statistical methods, and power calculation

In this open-label study, all subjects will receive a single IA Zilretta injection into each knee. Outcome measures will be collected at baseline, 6, 12 (primary) and 24 weeks post-treatment. A 24-week follow-up duration was selected to detect meaningful differences from standard of care (IA corticosteroids - TAcS) and long-term effects, while minimizing the variability that may occur further out from treatment. The overall type I error rate will be controlled with an alpha level of 0.0167 to account for three comparisons at the primary time point.

Based on the respective MDC₉₅ calculated from the standard error of the mean change for OARSI recommended physical performance¹, the effect size for this minimal detectable change is 0.392. To detect an effect size at least this large, with an adjusted alpha of 0.0167 and 80% power, a sample size of 60 would be required. To accommodate up to 14% dropout, we plan to recruit 70 subjects.

D. Subject Criteria (See Vulnerable Populations appendix, if applicable):

Enrollment will be comprised of 70 subjects age 30 and over with symptomatic bilateral knee OA. There will be no exclusions based on sex or ethnic group. Potential subjects will be identified through hospital records, referrals from physicians in the surrounding community, mass mailings, and advertisements posted in area clinics and businesses. Any study-related advertisements will be approved by the IRB prior to use. Subjects will be recruited based upon inclusion and exclusion criteria detailed below.

1. Inclusion Criteria

- Men and women age 30 years or older with symptomatic bilateral knee OA.

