NRS for Pain	X	X [‡]	X	X	X
Physical Performance Measures			X	X	X
AE/SAE Assessment		X	X	X	X

*Each visit must be within ± 5 days of the scheduled visit; [‡] may be combined with screening visit.

F. Risk/benefit assessment

The reference safety information for Zilretta for this study is the Zilretta USPI.

1. Physical risk:

Zilretta (triamcinolone acetonide extended-release injectable suspension) is indicated as an intra-articular injection for the management of pain due to knee OA. The most commonly reported adverse reactions (incidence $\geq 1\%$) in clinical studies included sinusitis (2%), cough (2%), contusions (2%) and joint swelling (3%). For additional details, please see Package Insert (<http://www.zilrettalabel.com/PI.pdf>). The website for Zilretta additionally lists: joint pain, headache, back pain, sore throat and runny nose, and bruising as common side effects of receiving a Zilretta injection.

The following is a list of other adverse events that can occur following injection of corticosteroids, although not reported following Zilretta.

- **Hypersensitivity Reactions:** Rare instances of anaphylaxis, including serious cases, have occurred in patients with hypersensitivity to corticosteroids. Serious cases of anaphylaxis, including death, have been reported in individuals receiving triamcinolone acetonide injection, regardless of the route of administration.
- **Joint Damage:** Intra-articular administration may result in damage to joint tissues.
- **Increased Risk of Infections:** Infection with any pathogen in any location of the body may be

associated with corticosteroids. Corticosteroids may increase the susceptibility to new infection and decrease resistance and the ability to localize infection. A marked increase in pain accompanied by local swelling, restriction of joint motion, fever, and malaise are suggestive of septic arthritis.

- **Alterations in Endocrine Function:** Corticosteroids can produce reversible hypothalamic-pituitary-adrenal axis suppression, with potential for adrenal insufficiency after withdrawal of treatment, which may persist for months.
 - **Cardiovascular and Renal Effects:** Corticosteroids can cause blood pressure elevation, salt, and water retention, and an increase potassium excretion.
 - **Increased Intraocular Pressure:** Corticosteroid use may be associated with increased intraocular pressure.

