If the subject is injured because of study participation, there will be no compensation for physical or non-physical injuries. No compensation will be available for any extra expenses that may be the result of research-related physical injuries including additional hospital bills, lost wages, travel expenses, etc. No compensation will be available for any non-physical injuries that may occur because of research participation, such as legal problems, problems with your finances or job, or damage to your reputation.

IV. Data Collection and Protection

A. Data Management and Security:

OARSI recommended¹⁰ physical performance measures (30-second chair stand time, 40m fast-paced walking time, stair ascent time) along with patient-reported physical function (KOOS-PS), quality of life (KOOS-QoL) and NRS pain data will be collected at baseline and 6, 12 and 24 weeks post-treatment. All data collected will remain confidential and accessible only to the research team. This data will be collected using a paper-based

CRF that will be transferred into two databases. These two databases contain the same collection points so reconciliation can be done to detect data entry errors.

Data regarding subject demographics, knee radiographs, OARSI recommended physical performance measures, and KOOS subscale responses and NRS pain will be gathered from subjects and numerically coded in sequential order with no patient identifiers. A master list with patient information and assigned study IDs will be stored in a separate password-protected file available only to the Principal Investigator and the Research Coordinator. Analyses will be performed on coded files. Physical files (e.g. questionnaires) will be stored in locked file cabinets in the offices of the Principal Investigator.

B. Sample / Specimen Collection: N/A

C. Tissue Banking Considerations: N/A

D. Procedures to protect subject confidentiality:

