Data regarding subject's demographic, knee radiographs, OARSI recommended physical performance measures, and KOOS subscale responses and NRS pain data will be obtained directly from subjects. All data will be coded with no information that could identify a subject. A master list with patient information and assigned study ID's will be stored in a password-protected file available only to the Principal Investigator and the Research Coordinator. Analyses will be performed on coded files. Physical files (e.g. questionnaires) will be stored in locked file cabinets in the office of the Principal Investigator.

E. Quality Assurance / Monitoring

Study staff will have proper qualifications for data entry and will receive training in data entry procedures to ensure data entered is of highest quality. Data will be entered by researchers into two separate databases developed for this study. Each database will contain the same collection points and then be reconciled to clean the data for analysis and outcome reports to the Principal Investigator. Data will be backed-up daily.

V. Data Analysis and Reporting

A. Statistical and Data Analysis:

The primary analysis will regard the change in the 3 OARSI-recommended physical performance measures between baseline and 12 weeks following injections. The three pre/post change scores will be assessed with one-sample t-test for matched pairs, using an alpha level of (.05/3) to determine statistical significant change.

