Differences between baseline and other timepoints and secondary/tertiary outcome measures will be assessed with repeated measures analyses, with time as a repeated factor to account for multiple comparisons over time. A soft-lock of the database will occur after the 6- and 12-week time points. The analyses of secondary and tertiary outcomes will involve the analyses of longitudinal data, collected at baseline, 6 weeks, 12 weeks, and 24 weeks. These response variables will be modeled using the framework of longitudinal mixed models. Each model will be based on two main effects: a random subject effect, and a fixed time effect consisting of four levels (baseline, 3 follow-up time points). The distribution of the secondary and tertiary outcome measures will be examined and transformation to a normal distribution will be performed if needed. We will use the Akaike information criterion to determine an appropriate variance/covariance structure. Each of the hypotheses of interest will be tested by examining appropriate contrasts and estimable linear forms in the overall mean and the main effects for time. Analyses will be conducted using SAS (Version 9.1.2). PROC MIXED will be used to fit the longitudinal models.

B. Outcome: We expect statistically significant and clinically meaningful improvement in physical performance, physical function, pain and quality of life 12 weeks following bilateral treatment with Zilretta.

C. Study results to subjects: The study will be registered on www.clinicaltrials.gov and results posted upon completion of the study.

D. Publication Plan: Results will be submitted for presentation at an appropriate conference and for publication in an appropriate journal for the topic of study.

VI. Bibliography / References / Literature Cited

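### The schedule of assessments shows no baseline visit for the physical performance tests, although the primary analysis is their change from baseline to 12 weeks

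*Combined protocol and SAP*

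**What the plan says.** Section II.E introduces the table as the visit-by-visit schedule of assessments and procedures. Its row "Physical Performance Measures" has marks at Visits 3, 4 and 5 only. The cells for Visit 1 (screening) and Visit 2 (treatment day) are empty. The footnotes give a visit window and allow items to be combined with screening; neither adds a baseline performance test.

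The text elsewhere asks for a baseline:

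- Section I.A, on outcomes generally: "Measurement and evaluation of outcomes at baseline, 6, 12 and 24 weeks will allow assessment of short and long-term effects".
- Section I.B (Preliminary Data) proposes to measure change in the three performance tests and the KOOS scales "at baseline and at intervals following bilateral knee injection of Zilretta".
- Section II.B opens its list of measurements with the OARSI performance measures and continues "patient-reported physical function, quality of life and pain at baseline, 6, 12 and 24 weeks".
- Section IV.A names the three tests first among the data that "will be collected at baseline and 6, 12 and 24 weeks post-treatment".

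The analysis in section V.A depends on that baseline: "The primary analysis will regard the change in the 3 OARSI-recommended physical performance measures between baseline and 12 weeks following injections". It continues: "The three pre/post change scores will be assessed with one-sample t-test for matched pairs". For the remaining comparisons: "Differences between baseline and other timepoints and secondary/tertiary outcome measures will be assessed with repeated measures analyses".

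**The concern.** The table is the only place in the protocol that assigns the performance tests to visits. The descriptions of the three tests in section II.E say how each is run but not when, whereas the NRS description in the same section does give its timing. For the primary outcome, then, the one operational instruction contains no measurement before treatment.

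The design makes this more serious than a gap in an ordinary schedule. There is a single arm and the primary test is paired within subject, so no control group can stand in for a missing baseline. Once a subject has been injected, the pre-treatment value is gone. If site staff or the case report form were set up from the table, none of the three primary change scores could be formed.

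**Working it through.** This is a comparison of table and text; the arithmetic only sizes the consequence.

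**1. Is the gap specific to this row?** Marks by visit, as the table reads:

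| Row | V1 | V2 | V3 | V4 | V5 | Total | At V1 or V2 |
|---|---|---|---|---|---|---|---|
| KOOS-PS and QoL | – | X | X | X | X | 4 | 1 |
| NRS pain | X | X | X | X | X | 5 | 2 |
| Physical performance | – | – | X | X | X | 3 | 0 |
| AE/SAE | – | X | X | X | X | 4 | 1 |

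The rows directly above and below keep their Visit 2 marks. The performance row has two empty cells and then three marks, which fits the five visit columns. A mark lost when the PDF was converted is therefore unlikely, though only the original page can rule it out.

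**2. Table against text.** The text requires four time points (baseline, 6, 12 and 24 weeks). The table provides three. The missing one is the baseline, and no footnote supplies it.

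**3. What depends on the missing mark.** Hypothesis 1 covers three tests at three follow-up times: 3 × 3 = 9 contrasts with baseline. Three of these, at 12 weeks, are primary. All nine need the baseline value.

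- Table followed: 0 of 70 subjects have a change score.
- Text followed: all 70 can have a baseline.

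**4. Room for partial misses, on the plan's own figures.** Section II.C requires 60 subjects and recruits 70 to allow for 14% dropout.

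- The recruitment figure reproduces: 60 / (1 − 0.14) = 69.8, rounded up to 70.
- The figure of 60 reproduces as a one-sided paired t-test with effect size 0.392 and alpha 0.0167 (power 0.8025 at n = 60).

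Subjects who could lack a baseline before the number falls below 60:

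| Dropout | Remaining | Spare |
|---|---|---|
| 14% | 70 × 0.86 = 60.2 | 0 whole subjects |
| 10% | 70 × 0.90 = 63 | 3 |
| 0% | 70 | 10 |

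These counts take 60 as given. The protocol does not state whether the test is one- or two-sided; the same calculation two-sided needs 71, which would leave nothing spare even with no dropout. That is a separate matter, and the present point does not depend on it.

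**The case against.** The best reply is that nobody would be misled. The baseline is stated repeatedly, including in the data-collection section, which lists the three tests by name, and the analysis section speaks of pre/post scores. No narrative text supports testing at follow-up only, so losing all 70 baselines is a worst case that requires staff to ignore several sections. This stands as a statement of likelihood: the blank is probably an oversight, and nothing here shows that data were lost. It does not remove the contradiction, and no other text supplies the missing mark.

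It can also be said that the order of test and injection is not really open, because section I.B contrasts baseline with the intervals after injection. That is right about intent. What remains unstated is the visit. Because Visit 2 may be combined with screening and is also the treatment visit, the sequence on the day deserves a line.

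The choice of Visit 2 is not dictated by the documents; it is the option most consistent with them.

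Finally, the spare-subject counts do not measure the defect, since a faulty schedule would tend to affect everyone or no one. That is fair. They bear only on scattered misses, and the conclusion does not need them.

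**Conclusion.** The concern holds and should be fixed before the schedule is used. As written, the schedule omits the measurement on which all three primary change scores, and all nine Hypothesis 1 contrasts, depend. The consequence is all or nothing: no primary result if the table governs, no loss if the text governs. The conclusion assumes that the table as read matches the original page, which the alignment of the neighbouring rows supports. The importance comes from the fact that the loss cannot be repaired, not from a belief that it is likely.

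**What to change.** Reconcile the table with sections I.A, I.B, II.B, IV.A and V.A:

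- Mark the performance measures at Visit 2 (or at the combined screening and treatment visit).
- Add a footnote that all three tests are completed before aspiration and injection.
- Confirm that the case report form and both databases have baseline fields for the three tests.

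Visit 2 fits the rest of the protocol. The KOOS baseline is marked there, and the 48-hour acetaminophen rule in section II.D.4 already covers the procedure visit and every follow-up visit but does not mention a separate screening visit. Testing at Visit 2 would therefore put the baseline under the same stated rule as the follow-up tests.

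The cost is one table mark and one footnote by amendment, plus the form check. No visit, staff time or procedure is added, because the text already commits to testing at baseline, and no sample-size figure changes.

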Compliance reports which include telephone screening forms for eligibility, radiographs, medication amenability and safety logs will be reviewed by the Principal Investigator on a weekly basis. Reports containing the proportion of subjects completing the intervention or prematurely terminating participation will be generated monthly.

Adverse event information will be collected at each visit and during all contacts with subjects. If an adverse event is reported to study staff, data including the type of event, onset/end dates, duration, and outcome will be collected and reported to the Principal Investigator. All adverse event information will be assessed by the Principal Investigator for severity, seriousness, and relationship to Zilretta, per the definitions below.

The Investigator is required to follow SAEs until resolution or withdrawal of consent. Resolution is defined as:

- A return to baseline for a pre-existing condition; or
- Resolved with or without residual effects; or
- The Investigator does not expect any further improvement or worsening of the event.

Reporting Serious Adverse Events:

An event that is serious must be recorded on the AE worksheet and requires expeditious handling to comply with regulatory requirements. Any adverse event classified as “serious” by the Investigator must be reported to the IRB within 24 hours of becoming aware of its occurrence. All serious adverse events in patients treated with Zilretta must also be reported to Flexion within 3 calendar days. The Investigator should attempt to collect as much information about the adverse event as needed to get a complete medical understanding and forward that information to Flexion as it becomes available.

All serious adverse events which are considered causally related to Zilretta (see definitions below) must be assessed for whether it is expected per the USPI. An unexpected event means that it is not described within the reference safety information (the Zilretta USPI) as associated with Zilretta. If an event is assessed as serious, related to Zilretta, and unexpected, it must be reported to the FDA according to 21CFR314.80

Safety Definitions:

Adverse Event (AE): An AE is any untoward medical occurrence in a patient or clinical investigation subject administered a pharmaceutical product and that does not necessarily have a causal relationship with this treatment. An AE can therefore be any unfavorable and unintended sign (including an abnormal laboratory finding), symptom, or disease temporally associated with the use of a medicinal (investigational) product, whether or not related to the medicinal (investigational) product, any clinically significant abnormality found on an ECG, laboratory test, or physical examination, or any worsening (i.e., any clinical significant adverse change in frequency and/or intensity) of a preexisting condition, which is temporally associated with the use of the medicinal (investigational) product

Serious Adverse Event (SAE): An SAE is any untoward medical occurrence that at any dose:

- Results in death,
- Is life-threatening, (“Life-threatening” refers to an event in which the patient was at substantial risk of death at the time of the event; it does not refer to an event which hypothetically might have caused death if it were more severe.)
- Requires inpatient hospitalization or prolongation of existing hospitalization.

- Note: Adverse events requiring hospitalizations that are less than 24 hours in duration do not meet this criterion. A scheduled hospitalization for an elective procedure or a pre-existing condition that has not worsened during participation in the study does not meet this criterion.
- Results in permanent or significant disability/incapacity; a substantial disruption of the patient's ability to carry out normal life functions.
- Is a congenital anomaly/birth defect.
- Is an important medical event: event that may not be immediately life-threatening or result in death or hospitalization but may jeopardize the patient or may require intervention to prevent one of the outcomes listed in the definition above.

Severity: the intensity of the adverse event. This is not the same as "serious," which is based on patient/event outcome or action criteria usually associated with events that pose a threat to a patient's life or functioning. The severity of AEs will be assessed according to the following definitions:

- Mild: the AE is noticeable to the patient and/or the Investigator, but does not interfere with routine activity.
- Moderate: the AE interferes with routine activity, but responds to symptomatic therapy or rest.
- Severe: the AE significantly limits the patient's ability to perform routine activities despite symptomatic therapy.

Causal Relationship: A medically-qualified Investigator must assess the relationship of any AE (including SAEs) to the use of the investigational product, as related or not related, based on clinical judgment and using all available information, and may include consideration of possible alternative causes of the AE, including the disease under treatment, pre-existing conditions, concomitant use of other drugs, and presence of environmental or genetic factors, the temporal association between drug exposure and onset of the AE, and whether the manifestations of the AE are consistent with known actions or toxicity of the investigational product. The causal relationship between the study medication and the AE will be assessed using one of the following categories:

- **Not Related:** An AE is not associated with study medication if:
 - Temporal relationship is lacking (e.g., the event did not occur within a reasonable time frame following administration of the study medication); or
 - Other causative factors more likely explain the event (e.g., a pre-existing condition, other concomitant treatments).
- **Related:** An AE is attributed to the study medication if:
 - There is a positive temporal relationship (e.g., the event occurred within a reasonable time frame following administration of study medication); and
 - The AE is more likely explained by the investigational product than by another cause (i.e., the AE shows a pattern consistent with previous knowledge of the investigational product or the class of the investigational product).

Data and Safety Monitoring Plan

The data will be reviewed by the study team and the Principal Investigator. The reviewed data include eligibility, data reconciliation and safety logs. There will also be reports containing the proportion of subjects completing the intervention or prematurely terminating participation . This will be done on a monthly basis.

III. Subject Participation

A. Recruitment:

Potential study subjects will be recruited from the clinics of the principal investigator and referring physicians, and using local advertising. Any study-related advertisements will be approved by the governing IRB prior to use. Subjects will be recruited based upon inclusion and exclusion criteria detailed above. Subjects will be compensated for their time and effort at follow-up visits.

Each subject will participate for up to 24 weeks. Enrollment is expected to take up to 6 months. Total study duration is expected to be at least 12 months.

B. Screening Interview/questionnaire:

Potential subjects who express interest in the study will be pre-screened by telephone. A script will be used to determine eligibility for the first screening clinic visit by study staff. Please reference Appendix A.

C. Informed consent process and timing of obtaining consent

Potential subjects who pass the initial screening criteria (telephone screen) will be asked to schedule a screening visit to provide written consent and possibly undergo screening procedures during a screening visit. Subjects will be informed that the study is voluntary and choosing not to participate will not affect their current treatment. They may request the opportunity to review the consent form with their physician and/or family members. Moreover, they will be fully informed of the purpose of the study and of the possible risks involved before providing their consent. Written, informed consent will be obtained and documented by an investigator or a study coordinator prior to initiation of study procedures. All subjects will be provided with a copy of the signed consent form.

D. Alternatives to Participation: The alternative to study participation is choosing not to participate and to continue with their current treatment plan.

E. Costs to Subjects: There will be no cost to subjects to participate in the study and no insurance will be billed as a part of the study procedures.

F. How new information will be conveyed to the study subject and how it will be documented: If any new information is to be provided to the study subject the informed consent form (ICF) will be amended and approved by the IRB. Each subject will then be re-consented using the newest revision of the ICF.

G. Payment, including a prorated plan for payment:

Subjects will be provided \$20 at Visit #2, \$20 at Visit #3, \$30 at Visit #4, and \$30 at the final Visit #5 (up to \$100 per subject) as compensation for their time. They additionally will be provided with parking validation for in-person visits. Moreover, subjects will be provided with encouragement during the study period, especially prior to and after each study visit by letting them know that their contributions are appreciated.

H. Payment for a research-related injury:

If the subject is injured because of study participation, there will be no compensation for physical or non-physical injuries. No compensation will be available for any extra expenses that may be the result of research-related physical injuries including additional hospital bills, lost wages, travel expenses, etc. No compensation will be available for any non-physical injuries that may occur because of research participation, such as legal problems, problems with your finances or job, or damage to your reputation.

IV. Data Collection and Protection

A. Data Management and Security:

OARSI recommended¹⁰ physical performance measures (30-second chair stand time, 40m fast-paced walking time, stair ascent time) along with patient-reported physical function (KOOS-PS), quality of life (KOOS-QoL) and NRS pain data will be collected at baseline and 6, 12 and 24 weeks post-treatment. All data collected will remain confidential and accessible only to the research team. This data will be collected using a paper-based

CRF that will be transferred into two databases. These two databases contain the same collection points so reconciliation can be done to detect data entry errors.

Data regarding subject demographics, knee radiographs, OARSI recommended physical performance measures, and KOOS subscale responses and NRS pain will be gathered from subjects and numerically coded in sequential order with no patient identifiers. A master list with patient information and assigned study IDs will be stored in a separate password-protected file available only to the Principal Investigator and the Research Coordinator. Analyses will be performed on coded files. Physical files (e.g. questionnaires) will be stored in locked file cabinets in the offices of the Principal Investigator.

B. Sample / Specimen Collection: N/A

C. Tissue Banking Considerations: N/A

D. Procedures to protect subject confidentiality:

Data regarding subject's demographic, knee radiographs, OARSI recommended physical performance measures, and KOOS subscale responses and NRS pain data will be obtained directly from subjects. All data will be coded with no information that could identify a subject. A master list with patient information and assigned study ID's will be stored in a password-protected file available only to the Principal Investigator and the Research Coordinator. Analyses will be performed on coded files. Physical files (e.g. questionnaires) will be stored in locked file cabinets in the office of the Principal Investigator.

E. Quality Assurance / Monitoring

Study staff will have proper qualifications for data entry and will receive training in data entry procedures to ensure data entered is of highest quality. Data will be entered by researchers into two separate databases developed for this study. Each database will contain the same collection points and then be reconciled to clean the data for analysis and outcome reports to the Principal Investigator. Data will be backed-up daily.

V. Data Analysis and Reporting

A. Statistical and Data Analysis:

The primary analysis will regard the change in the 3 OARSI-recommended physical performance measures between baseline and 12 weeks following injections. The three pre/post change scores will be assessed with one-sample t-test for matched pairs, using an alpha level of (.05/3) to determine statistical significant change.

Differences between baseline and other timepoints and secondary/tertiary outcome measures will be assessed with repeated measures analyses, with time as a repeated factor to account for multiple comparisons over time. A soft-lock of the database will occur after the 6- and 12-week time points. The analyses of secondary and tertiary outcomes will involve the analyses of longitudinal data, collected at baseline, 6 weeks, 12 weeks, and 24 weeks. These response variables will be modeled using the framework of longitudinal mixed models. Each model will be based on two main effects: a random subject effect, and a fixed time effect consisting of four levels (baseline, 3 follow-up time points). The distribution of the secondary and tertiary outcome measures will be examined and transformation to a normal distribution will be performed if needed. We will use the Akaike information criterion to determine an appropriate variance/covariance structure. Each of the hypotheses of interest will be tested by examining appropriate contrasts and estimable linear forms in the overall mean and the main effects for time. Analyses will be conducted using SAS (Version 9.1.2). PROC MIXED will be used to fit the longitudinal models.

B. Outcome: We expect statistically significant and clinically meaningful improvement in physical performance, physical function, pain and quality of life 12 weeks following bilateral treatment with Zilretta.

C. Study results to subjects: The study will be registered on www.clinicaltrials.gov and results posted upon completion of the study.

D. Publication Plan: Results will be submitted for presentation at an appropriate conference and for publication in an appropriate journal for the topic of study.

VI. Bibliography / References / Literature Cited

